7.5.4 Electrocardiograms

12-Lead ECG results and change from baseline will be summarized for each visit by treatment group using mean, standard deviation, minimum, maximum and median. Baseline is defined as the last available measurement prior to the first dose.

Number and percent of patients with normal, not clinically significant abnormal and clinically significant abnormal results for the 12 lead ECG will be tabulated by treatment arm and visit.

QTc will be calculated using Fridericia Formula, $QTcF = QT \text{ interval} / RR^{0.33}$.

All ECG results will be provided in a listing.

7.5.5 Physical Examination

Any abnormal findings/conditions identified during the physical examination are reported in the medical history form or AE form. As a consequence, no separate physical examination listing can be produced.

7.5.6 Pregnancy

Not applicable.

7.5.7 Other Safety-Related Observations

The number and percentage of patients falling in each category of the performance status ECOG score will be listed.

7.6 Analysis of Exploratory Endpoint

Not applicable.

7.7 Analysis of Pharmaco-kinetic

Not applicable.

7.8 Analysis of Pharmaco-dynamic

Not applicable.

7.9 Subgroups of Interest

Subgroup analyses of TPP will be conducted to assess the consistency of the treatment effect across the following subgroups of interest:

- Age category (less than 65 years old versus 65 years old or more);
- ECOG Performance Status (0 versus 1) at baseline;
- Gleason score (less than 8 versus 8 or more) at initial diagnosis;
- Disease location (bone only, versus soft tissue only, versus both bone and soft tissue) at baseline;
- Baseline PSA value (at or below overall median versus above overall median);
- Volume of disease at baseline (low versus high)
- Prior docetaxel use (yes versus no)
- Previous use of ADT or orchiectomy (yes versus no)

7.10 Other Analyses

Assessments affected by COVID-19 will be summarized and listed.

7.11 Interim Analysis (and Early Discontinuation of the Clinical Study)

An interim analysis is planned to occur after approximately 60 PSA progression events (about 80% of the total planned events) are observed. TPP will be tested for efficacy according to the O'Brien-Fleming boundary as implemented by Lan-DeMets alpha spending function [Lan-DeMets, 1983]. The IDMC may recommend terminating the trial at the interim analysis based on statistically significant TPP results favoring enzalutamide. In case IDMC recommend continuing the trial after the interim analysis, the final TPP analysis will be conducted when total PSA progression events reach 75. Data cut-off dates will be set when the planned number of events is reached for the interim and final analyses. If the exact number of events at interim and final analyses are different than planned, the significance level will be adjusted accordingly, based on the O'Brien-Fleming method with a Lan-DeMets alpha spending function.

The interim analysis will be conducted by independent data analysis group (DAC) with randomized treatment assignments and reviewed by the IDMC. The full procedures for IDMC and interim analysis will be described in a separate IDMC charter and Interim Analysis Plan.

7.12 Handling of Missing Data, Outliers, Visit Windows, and Other Information

The baseline measurement is the last measurement taken prior to initial study drug administration. Both date and time of drug administration and measurement should be considered to identify the baseline value. If the time is not available, then date only will be used and it will be considered that assessments on day 1 are done pre-dose.

Change from baseline is defined as (post baseline value - baseline value).

To calculate time interval duration, a month is 30.4375 days and a year 365.25 days. Duration expressed in years or months are rounded up to 1 significant digit. The duration between 2 dates d1 and d2 is (d2-d1+1) in days (with d1 before d2).

Treatment day and study day will be calculated in reference to the date of the first dose of study drug. Treatment Day 1 corresponds to the date the patient received the first dose of study drug. For assessments conducted on or after the date of the first dose of study drug, treatment day will be calculated as (assessment date - date of first dose of study drug) + 1. There will be no Treatment Day 0.

Unless otherwise specified, the date of study drug discontinuation refers to the study drug last dose date. Should that date be partially missing, the end of treatment date recorded on the end of treatment form will be used.

Time to event endpoints will be based on the actual date of event rather than visit date. The date of randomization will always be considered as the start date for the time interval.

For laboratory results collected as < or > a numeric value, 0.0000000001 will be subtracted or added, respectively, to the value unless otherwise specified.

Percentages will be calculated based on the number of patients with non-missing data as the denominator unless otherwise specified.

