4 SAMPLE SIZE

As originally planned, approximately 180 Chinese subjects will be randomized in the study (120 subjects in enzalutamide+ADT arm and 60 subjects in placebo+ADT arm).

The final analysis of TPP will be conducted with a planned 75 PSA progression events, based on the following considerations:

- A target HR is 0.5. The expected median TPP for the ADT arm is 9 months as measured from the date of randomization. A target HR of 0.5 corresponds to approximately 100% increase in median TPP for the enzalutamide plus ADT arm relative to the placebo plus ADT arm (approximately 18 versus 9 months, with 10% dropout rate).
- The planned 75 PSA progression events (a 25% increase in PSA and at least 2 ng/mL above the nadir according to Prostate Cancer Clinical Trials Working Group 3 criteria) provides approximately 80% power to detect a target HR of 0.5 based on a 2-sided log-rank test and overall significance level of 0.05.

- There will be 1 interim analysis at 80% of the total planned events (about 60 PSA progression events), providing 61% power to demonstrate superiority at a 2-sided alpha of 0.0244.

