- The null hypothesis: TPP for Placebo+ADT and Enzalutamide +ADT are not different
- The alternative hypothesis: TPP for Placebo+ADT and Enzalutamide+ADT are different

The following SAS code will be used to compute the Kaplan-Meier estimates and curves, and the stratified log-rank test:

```
PROC LIFETEST DATA=INPUT  
    ATRISK  
    PLOTS=SURVIVAL(CB)  
    OUTSURV=SURVPL  
    ALPHA=0.05  
    ALPHAQT=0.05 METHOD=KM;  
    TIME AVAL*CNSR(1);  
    STRATA STRATUM1 STRATUM2/ GROUP=TREATMENT;  
    RUN;
```

where INPUT is the input dataset

AVAL is the time to the event variable,

CNSR is 0 (patients with events) or 1 (patients without event, i.e. patient censored)

STRATUM is the stratification variable (volume of disease and prior docetaxel use)

TREATMENT is the treatment variable

Kaplan-Meier methods will be used to estimate the distribution of TPP events by treatment group. The median TPP will be estimated using the corresponding 50th percentile of Kaplan-Meier estimates. A two-sided 95% confidence interval will be provided for this estimate by use of the Brookmeyer and Crowley method. A Kaplan-Meier plot by treatment group will be presented. The estimates of the event free rate on a 3-monthly basis up to 1 year and every 6 months thereafter will be summarized by treatment group, as long as at least 10 patients are at risk.

The benefit of Enzalutamide+ADT compared to placebo+ADT will be summarized by a single HR with its 95% CI based on a Cox regression model stratified for the prior docetaxel use and disease volume. The null and alternative hypotheses regarding TPP can be rephrased in terms of the HR ($\lambda_{\text{ArmA}} / \lambda_{\text{ArmB}}$), where λ_{ArmA} represents the hazard of TPP for Enzalutamide+ADT and λ_{ArmB} represents the hazard of TPP for placebo+ADT. A HR of < 1 indicates that the

TTTP is prolonged for patients randomized to Enzalutamide+ADT compared with patients randomized to placebo+ADT. The null and alternative hypotheses, respectively, can be written as follows:

$$H_0: \frac{\lambda_{ArmA}}{\lambda_{ArmB}} = 1 \quad H_1: \frac{\lambda_{ArmA}}{\lambda_{ArmB}} \neq 1$$

The estimated HR of Enzalutamide+ADT to placebo+ADT, and its 95% confidence interval will be provided.

SAS PROC PHREG will be used for the analysis with the “DISCRETE” option for tie breaker as follows:

```
PROC PHREG DATA = INPUT;  
  MODEL AVAL*CNSR(1) = TREATMENT / TIES=DISCRETE;  
  STRATA STRATUM1 STRATUM2;  
  RUN;
```

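### The rounding rule for durations in SAP 7.12 (up, to one significant digit) cannot sensibly be followed and needs a one-sentence correction; it is probably a slip for one decimal place

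*SAP*

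**What the plan says.** SAP 7.12 sets general derivation conventions. It gives the conversion, "To calculate time interval duration, a month is 30.4375 days and a year 365.25 days", and then the rounding rule, "Duration expressed in years or months are rounded up to 1 significant digit". The next sentence defines the interval between two dates in days, counting both end dates. The section later adds: "Time to event endpoints will be based on the actual date of event rather than visit date". It does not say whether the rounding is for derivation or for display, and the protocol has no competing rule.

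Elsewhere the SAP plans and reports on a scale of months:

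- Section 4 gives the planned medians for time to PSA progression (TTPP) as "approximately 18 versus 9 months, with 10% dropout rate".
- Section 7.4.1 asks for "The estimates of the event free rate on a 3-monthly basis up to 1 year and every 6 months thereafter", which means 3, 6, 9, 12 and 18 months and onward while at least 10 patients are at risk.
- The SAS code in 7.4.1 uses a variable described only by "AVAL is the time to the event variable", with no unit and no rounding step.
- Section 6.4 gives exposure in months as days divided by 30.4375, also with no rounding step.

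**The concern.** One significant digit leaves whole months up to 9 and whole tens after that. Rounding upward sends everything above 10 and up to 20 months to 20. Neither the planned enzalutamide median of 18 nor the 12- and 18-month landmarks can be written under such a rule.

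The sentence sits between two derivation rules and carries no display-only qualifier. A programmer who derives event times in months therefore finds one written rounding instruction, and it is this one. What is at stake is the description of the primary result (medians and landmark rates) and other summaries in months, such as disease duration at baseline in SAP 7.2.3. A programmer who silently substitutes a sensible rule would depart from the SAP without a record, although SAP section 1 requires changes from the planned analyses to be justified in the study report.

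**Working it through.** **Inputs.** From SAP section 4: medians 18 and 9 months, hazard ratio (HR) 0.5, 120:60 allocation, 75 final and 60 interim events. From SAP 7.4.1: two-sided levels 0.0244 and 0.0429, and the landmark times. From SAP 7.12: 30.4375 days per month. From the protocol synopsis: 15 months of recruitment. Exponential curves are my assumption.

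**1. The plan's own figures.** Power = Φ(√(events × 2/3 × 1/3) × ln 2 − z).

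- 75 events at 0.05: √16.67 × 0.693 − 1.960 = 0.870, so 80.8% (plan: about 80%).
- 60 events at 0.0244: √13.33 × 0.693 − 2.250 = 0.281, so 61.0% (plan: 61%).
- O'Brien-Fleming-type Lan-DeMets spending at information 0.80 gives 0.0244 and 0.0429, with group-sequential power 80.0%.

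All of these reproduce, and none depends on the rounding sentence.

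**2. The rule taken literally.** For a duration x, let k = 10^floor(log10 x); the rounded value is k × ceiling(x/k).

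| x (months) | Up, 1 significant digit | 1 decimal place |
|---|---|---|
| 9.0 | 9 | 9.0 |
| 9.2 | 10 | 9.2 |
| 12.4 | 20 | 12.4 |
| 18.0 | 20 | 18.0 |
| 18.3 | 20 | 18.3 |

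Reading 'rounded up' loosely as 'rounded to nearest' does not rescue it: 18.0 and 18.3 still become 20.

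**3. If applied to each patient's time before Kaplan-Meier estimation.** No event could fall between 10 and 20 months, so the curve is flat from 10 until 20. The 12- and 18-month rates both equal S(10). With S(t) = 0.5^(t/median):

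| Event-free rate | Enzalutamide | Placebo |
|---|---|---|
| S(10), reported at both 12 and 18 months | 0.5^(10/18) = 68.0% | 0.5^(10/9) = 46.3% |
| S(12), correct at 12 months | 0.5^(12/18) = 63.0% | 0.5^(12/9) = 39.7% |
| S(18), correct at 18 months | 50.0% | 25.0% |

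The overstatement is 5.0 and 6.6 percentage points at 12 months, and 18.0 and 21.3 points at 18 months.

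**4. Effect on the test in that worst case.** I compared rounded and unrounded times in 1,000 simulated trials (15-month uniform accrual, data cut at the 75th event, unstratified log-rank test). Dropout of 10% per year is an assumption, because the documents give 10% without a time unit.

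| | Unrounded | Literal rule on patient times |
|---|---|---|
| Rejection at the final level | 82.3% | 82.2% |
| Mean z | −3.06 | −3.02 |
| HR (one-step log-rank approximation) | 0.45 | 0.45 |
| 12-month rate | 63.0% vs 39.4% | 68.6% vs 46.9% |
| 18-month rate | 49.6% vs 25.1% | 68.6% vs 46.9% |

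The formula in step 1 at level 0.0429 alone gives 79.0%, so the simulated rejection rate serves only for the comparison between columns.

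**5. If used for display only.** Estimation is untouched, so the landmark rates do not change. A median of 18.0 would print as 20, and 9.0 would print as 9.

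**6. If one decimal place was meant.** 557 days / 30.4375 = 18.2998, shown as 18.3. Even rounding patient times up to one decimal leaves the simulated rates at 63.1% vs 39.5% (12 months) and 49.8% vs 25.3% (18 months). The typical estimable medians are then 16.3 vs 9.1, against 16.3 vs 9.0 unrounded.

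**The case against.** The strongest reply is that the sentence is an obvious drafting slip with no practical effect. The planned median of 18 months and the landmarks at 12 and 18 months show that its authors did not mean one significant digit. The neighbouring text works in days and actual dates, the SAS code has no rounding step, and the exposure formula in months has none either. The exposure milestones in SAP 7.3.1 are set in days. With one decimal place nothing material changes.

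Most of this stands, and it limits the point. A reader might infer that the trial's medians and landmark rates will come out wrong, or that the rule governs the primary time variable and every exposure summary. The documents do not support either inference. The first needs the rule to be both taken literally and applied to patient-level times before estimation, and the SAP does not instruct the second step. The rule covers only durations expressed in years or months, and no section says the analysis variable is in months.

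What the reply does not remove is the wording itself. It is an operative instruction, nothing in either document overrides it, and nothing says that analyses use unrounded times.

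**Conclusion.** The sentence is wrong as written and should be corrected; the severity is minor. The certain part is the wording: a literal reading gives 20 for 18.3 and 10 for 9.2, which contradicts the scale on which the endpoint is planned and reported. The distortion of the 12- and 18-month rates is conditional on literal, patient-level use. Its size on the planned curves rests on exponential times with medians 18 and 9, and does not depend on any dropout assumption.

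A reader might also infer a threat to the primary test. There is none of substance: the stated power and boundaries do not use the sentence, display-only use leaves the test untouched, and even the worst case moves simulated rejection by only 0.1 percentage point.

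**What to change.** Replace the rounding sentence in SAP 7.12 with: 'Time-to-event and other durations are derived and analysed unrounded from days (days/30.4375 for months, days/365.25 for years); results in months or years are rounded to one decimal place for display only.'

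The cost is one sentence in a version-controlled SAP revision, which SAP section 1 allows before database hard lock. No data collection changes. Programs need a check that no rounding is applied to the analysis time variable, and need changing only if it is.

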7.12.1 Missing Data

As a general principle, no imputation of missing data will be done. Exceptions are the start and stop dates of AEs, previous and concomitant medications, and also the date of initial diagnosis (to estimate the relative study day to calculate cancer duration) and dates of cancer treatment (e.g. previous procedure, previous radiotherapy, etc...), the last dose date and the date of death.

The imputed dates will be used to allocate the relative study day of the medication/therapies and AEs to treatment, in addition to determining whether an AE is/is not treatment emergent.

Cases where the onset date of an AE is (partially) missing, will be addressed during the data review meeting in order to determine whether the AE must be considered treatment emergent or not.

Imputation on missing non-prostate cancer related medication dates (to categorize them as previous medications or concomitant medications, or post treatment) and AE dates (to categorize them as TEAE or not) and SSE dates will be done as follows:

- Incomplete Start Day and the corresponding end date is complete: use the later of (first day of the month, first dosing day if first dosing month); but if later than the end date, then impute the start day as the day of the end date.
- Incomplete Start Day and End Day is incomplete: use the later of (first day of the month, first dosing day if first dosing month).
- Incomplete End Day: use the earliest of (last day of the month, day of the 30-day follow-up visit if it is the month of the 30-day follow-up visit);
- Incomplete Month or Year: no imputation.

Imputation on missing date of initial diagnosis (cancer duration) and prior cancer treatment, including prostate cancer drug medication/therapies, (e.g. start date, stop date, or date of procedure) will be done as follows:

- Incomplete Day: use the 15th day of the month, if month/year is before first dosing or after last dosing (-for start date imputation- but if later than the end date, then impute the start day as the day of the end date; -for end date imputation- but if earlier than the start date, then impute the end day as the day of the start date).
- Incomplete Month: use 1st of July if the Year is before Year of first dosing, otherwise missing.
- Incomplete Year: no imputation, the derived variable is considered to be missing.

If (partially) missing, the last dose date of treatment will be imputed as follows:

- Incomplete Day: use the earliest of (last day of the month, end of treatment [form] day, day of the 30-day follow-up visit);

- Incomplete Month or Year: no imputation

If partially missing, the date of death will be imputed as follows:

- Incomplete Day: use the earliest of (last day of the month, end of study [form] day)
- Incomplete Month or Year: use the earliest possible date (next day of the last visit/contact date the participant is known to be alive).

Imputation methods will not be used to determine other endpoints.

Listings will always show the original date information without imputation, and derived parameters requiring imputation (e.g., TEAE indicator, start day, end day, study day) will be flagged.

7.12.2 Outliers

All values will be included in the analyses.

7.12.3 Visit Windows

Visit windows are allowed for certain visits per the schedule of assessments. Patient data will not be excluded from analyses due to the patient's failure to comply with the visit schedule and unscheduled visits are also assigned analysis visit window based on the visit day.

For summary tables reporting results by visit, analyses of efficacy and safety variables will be performed according to the analysis visit windows described in the following Table 8.

Table 8 Analysis Visit Windows

Visit Day Interval	Scheduled Visit	Analysis Visit*
For double-blind treatment period:		
-28<=Visit Day<1	Week -4 to -1 (Day -28 to -1)	Screening
Up to Day 1	Week 1 (Day 1)	Baseline
Day 2 - Day 43	Week 5 (Day 29)	Week 5
Day 44 - Day 71	Week 9 (Day 57)	Week 9
Day 72 - Day 99	Week 13 (Day 85)	Week 13
For the next visits after week 13 during the double-blind treatment period:		
Week X = Week (i*4+13) (i=1,2,3,...)		
Week X target day = i*4*7 + 85 (i=1,2,3,...)		
Week X (Wk X target day - 13 days ; Wk X target day + 14 days)		
Special case for Testosterone, CT/MRI and Bone Scan, Chest X-ray or Chest CT or MRI, QoL Assessment and ECOG Performance Status:		
Week 13 (Day 85) day interval is Day 72 - Day 127 and for the visits after Week13:		
Week X = Week (i*12+13) (i=1,2,3,...)		
Week X target day = i*12*7 + 85 (i=1,2,3,...)		
Week X (Wk X target day - 41 days ; Wk X target day + 42 days)		
However for the (last) visit during the double-blind treatment period, i.e. the last dose day of study drug is recorded,		
the upper boundary of the analysis visit window is 3 days after the last dose day, e.g.:		
Week X = Week (i*4+13) (i=0,1,2,3,...)		
Week X target day = i*4*7 + 85 (i=0,1,2,3,...)		
Week X (Wk X target day - 13 days ; last dose day + 3 days)		
Special case for Testosterone, CT/MRI and Bone Scan, Chest X-ray or Chest CT or MRI, QoL Assessment and ECOG Performance Status:		
Week 13 (Day 85) day interval is Day 72 - Day 127 and for the visits after Week13:		
Week X = Week (i*12+13) (i=1,2,3,...)		
Week X target day = i*12*7 + 85 (i=1,2,3,...)		
Week X (Wk X target day - 41 days ; last dose day + 3 days)		
(last double-blind dose day + 4 ; last double-blind dose day + 42 if not entering open-label phase) or (last double-blind dose day + 4, up to CRF collected last visit prior to the CRF collected open-label phase day 1 visit)	last double-blind dose day + 30 days	30 Day Safety F-up (after last dose or prior to new therapy)
For open-label phase: all eCRF collected Open Label visits		

Visit Day Interval	Scheduled Visit	Analysis Visit*
eCRF collected open-label day 1 visit up to open-label dose Day 1, or up to open-label informed consent date if not dosed	Open Label Phase Week 1 (Day 1)	Open Label Phase Baseline
Day 2 - Day 43	Open Label Phase Week 5 (Day 29)	Open Label Phase Week 5
Day 44 - Day 127	Open Label Phase Week 13 (Day 85)	Open Label Phase Week 13

For the next visits after week 13 during the open-label phase:
 
Open Label Phase Week X = Week (i*12+13) (i=1,2,3,...)
 
Open Label Phase Week X target day = i*12*7 + 85 (i=1,2,3,...)
 
Open Label Phase Week X (Wk X target day - 41 days ; Wk X target day + 42 days)
		

However for the (last) visit during the open-label treatment period, i.e. the last dose day of study drug is recorded,
 
the upper boundary of the analysis visit window is 5 days after the last dose day, e.g.:
 
Open Label Phase Week X = Week (i*12+13) (i=0,1,2,3,...)
 
Open Label Phase Week X target day = i*12*7 + 85 (i=0,1,2,3,...)
 
Open Label Phase Week X (Wk X target day - 41 days ; last dose day + 5 days)
		
(last open-label dose day + 6, last assessment)	last open-label dose day + 30 days	Open Label Phase 30 Day Safety F-up (after last dose or prior to new therapy)

For long-term follow-up visits conducted after double-blind treatment period or open-label phase:
 
Patients who end treatment before the data analysis cut-off date and have long-term (LT) follow-up visits,
 
have visits every 12 weeks after last dose day:
 
LT F-up j = j*12 weeks visit after last dose day (j=1,2,3,...)
 
LT F-up j target day = j*12*7 + last dose day (j=1,2,3,...)
 
LT F-up j (j*12*7 + last dose day - 41 ; j*12*7 + last dose day + 42)
		

F-up: follow-up; WK: Week

*At OL1 Visit (open-label day 1), the following assessments (ECG; vital signs; physical examination; clinical labs; ECOG) do not need to be repeated if they were completed within 7 days in Safety Follow-up Visit during double blind treatment period, and the corresponding data captured in Safety Follow-up Visit could be captured repeatedly in OL1 CRF forms, thus those assessments will serve the analysis needs for both double blind treatment period and open-label phase where applicable. And “open-label” will be reflected in the open-label phase visits’ label as applicable, e.g. OLP Baseline, Open Label Week X, etc..

In the case of multiple observations in the same analysis visit window, the observation which is closest to the target date will be used. If the observations have the same distance to the target visit day, the latest one will be used (using date, and time if available). Should there be two assessments documented at the same time due to the repetition of analysis of the same sample, the one reported as scheduled will be used, but for the exceptional case where both the two

assessments are reported as scheduled the primary assessment (i.e. not the repetition assessment) will be used.

